9. SAFETY EVALUATION

Safety summaries will be presented overall and grouped by treatment group. Continuous variables will be summarized using the following descriptive statistics: n (non-missing sample size), mean, standard deviation, median, maximum and minimum. All categorical measures will be summarized by the frequency and percentages of observed levels. The denominator for the percentages may be based on the number of non-missing observations for an assessment or on the number of subjects in a population. This will be described for each table. Note that tables containing an asterisk (*) in the title indicate tables that will be provided to the PI for publication.

9.1. Demographic and Other Baseline Characteristics

The following will be summarized for all enrolled subjects. Summaries of sex, ethnicity, race, cUTI type, age group (< 65, ≥ 65 years), age, BMI, and baseline CrCl will be presented by site ([Table 11](#) and [Table 12](#)) or by treatment group and overall ([Table 13](#) and [Table 14](#)). Ethnicity is categorized as Hispanic or Latino, or not Hispanic and not Latino. In accordance with NIH reporting policy, subjects may self-designate as belonging to more than one race or may refuse to identify a race, the latter reflected in the eCRF as “No” to each racial option.

The following will be summarized for subjects in the micro-ITT population. Summaries of age, sex, race, BMI, cUTI type, baseline CrCl, medical history, and susceptibility to select pathogens will be presented by treatment group and overall ([Table 15](#)). [Table 16](#) will present summaries of these baseline characteristics by treatment group and missing composite cure status. A pie chart showing the distribution of all uropathogens is provided in [Figure 2](#).

Demographic information for individual subjects will be provided in [Listing 5](#).

9.1.1. Prior and Concurrent Illnesses and Medical Conditions

Summaries of subject’s medical history will be presented by MedDRA® system organ class (SOC) and treatment group for all enrolled subjects ([Table 17](#)).

Individual subject listings for all reported medical history including prior and concurrent medical conditions will be presented in [Listing 6](#).

9.1.2. Prior and Concurrent Medications

All concomitant medications taken within 30 days of signing the informed consent or during the study period will be recorded. Concomitant medications will be coded to the Anatomical Therapeutic Classification (ATC) using the WHO Drug Dictionary. The use of concomitant medications during the study will be summarized by ATC1 and ATC2 code and treatment group for subjects in the Safety population ([Table 53](#)). A listing of concomitant medications will be presented in [Listing 19](#).

9.2. Measurements of Treatment Compliance

Subjects will be directly observed at the time of first dosing by a member of the clinical research team who is trained to administer the study drug. Administration will be documented on the source document and entered in the eCRF. A pill/sachet count will be performed.

The number of enrolled subjects receiving the first dose of study product will be tabulated by site and treatment group ([Table 8](#)). The number of doses of study product administered will be presented by treatment

group (Table 9), and as part of the subject disposition table (Table 6). Listing 7 provides a subject listing of missed doses along with a list of extra doses if applicable.

9.3. Adverse Events

All summaries of solicited AEs will be presented for the Safety Population and repeated for the Fosfomycin Safety Population. Summaries of unsolicited AEs will only be provided for the Fosfomycin Safety Population.

When calculating the incidence of AEs over multiple days (i.e., on a per subject basis), each subject will only be counted once and any repetitions of AEs within a subject will be ignored; the denominator will be the total population size on the first day of the time period (Day 1). For tabulation of AEs by day, the denominator will be the number of subjects enrolled and not withdrawn from the study by the day being described. All AEs reported will be included in the summaries and analyses.

A summary of all AEs will be provided in Table 34 for the Fosfomycin safety population. A summary of all AEs that occurred in $\geq 5\%$ of subjects in the Fosfomycin safety population in any treatment group will be provided in Table 35. A summary of any grade 2 and above solicited AE, any AE that led to discontinuation of the study product, and any AESI will be provided in Table 36. Among subjects who took at least two doses of fosfomycin, the frequency and percentage of subjects who experienced at least one solicited AE, unsolicited AE, and SAE, and subjects who discontinued fosfomycin in any treatment strategy will be summarized in Table 37.

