#### 9.2.2. Solicited Adverse Events

Solicited AEs are AEs that are common following administration of these types of antibiotics. The solicited AEs will be collected after first dose of study product is given and until the EOT. If subject is on fosfomycin, solicited AEs will be collected for 2 days after last dose of fosfomycin or until EOT, whichever occurs last.

Only grade 2 and above solicited AEs will be reported.

The following Toxicity Grading Scales will be used to grade solicited AEs:

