9.3.1. Solicited Events and Symptoms

Solicited AEs are AEs that are common following administration of these types of antibiotics. The solicited AEs will be collected after first dose of study product is given and until the EOT. If a subject is on fosfomycin, solicited AEs will be collected for 2 days after last dose of fosfomycin or until EOT, whichever occurs later.

Solicited events were recorded for trial Days 1-12, or until study completion or termination, as the maximum severity for each day. Only grade 2 and above solicited AEs will be reported. Target solicited events include insomnia, headache, dizziness, nausea, vomiting, constipation, diarrhea, back pain, rhinitis, pharyngitis, allergic reaction, candidiasis. The solicited events were measured by grading scales as defined in Table 3.

When calculating the incidence of solicited events, each subject will be counted once at the highest severity per day, and any repetitions will be ignored. For summaries presented separately for each treatment group, the denominator will be the number of subjects who received at least one dose of the treatment with non-missing data for the event summarized.

The number and percentage of subjects reporting at least one solicited adverse event of moderate severity or higher will be summarized for each solicited symptom and any symptom in Table 38 for the Safety analysis population. For each event, the denominator is the number of subjects in the applicable treatment group who received at least one dose of study product with non-missing data for the specific event. The 95% CIs calculated using Wilson methodology from a binomial distribution (SAS Proc Freq with a binomial option) will be presented. This analysis will be repeated in Table 39 to include subjects in the Fosfomycin safety analysis population who are those who received at least two doses of Fosfomycin.

For each systemic and any systemic event, the maximum severity over 12 days after the first dose will be summarized. The number and percentage of subjects reporting each event will be summarized by the maximum severity and treatment group. For each event, the denominator is the number of subjects who received the applicable treatment with non-missing data for the specific event. The 95% CI calculated using

Wilson methodology from a binomial distribution (SAS Proc Freq with a binomial option) will be presented [Table 40](#) for the Safety population and [Table 41](#) for the Fosfomycin safety population.

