9.3.2. Unsolicited Adverse Events

The unsolicited AEs will be collected only in the Fosfomycin Safety Population which includes subjects who receive at least two doses of Fosfomycin from the time of second dose of fosfomycin until EOT or 2 days after last dose of fosfomycin whichever occurs later. The grading scale for AESIs is provided in [Table 4](#).

The number and percentage of subjects reporting at least one unsolicited AE will be summarized by MedDRA SOC and preferred term (PT). A 95% CI will be presented for the percentage of subjects reporting any unsolicited AE (serious or non-serious) for each MedDRA SOC and PT ([Table 46](#)).

The following summaries for unsolicited AEs will be presented by MedDRA SOC, PT, and treatment group:

- Incidence of AEs by severity and relationship to study product ([Table 47](#));
- Incidence of non-serious, related AEs by severity ([Table 48](#));
- Subject listing of non-serious AEs of moderate or greater severity ([Table 51](#));
- Bar chart displaying total frequency of AEs by severity, MedDRA SOC and treatment group ([Figure 5](#));
- Bar chart displaying incidence of AEs by severity, MedDRA SOC and treatment group ([Figure 6](#));

[Listing 11](#) will present details of unsolicited AEs including Subject ID, AE description, AE onset date/end date, relationship to treatment, alternate etiology if not related, outcome, and duration of event (days).

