| | Severe | x/x (x) | x/x (x) | x/x (x) | x/x (x) | x/x (x) | x/x (x) | x/x (x) | x/x (x) | x/x (x) | x/x (x) | x/x (x) | x/x (x) | x/x (x) | x/x (x) |

Note: N = Number of subjects in the Safety Population in the respective treatment group with severity grades collected for each solicited symptom on the respective day(s). n = Number of subjects reporting a corresponding severity for a given symptom for that day.

Table 43: Number and Percentage of Subjects Experiencing Solicited Events by Symptom, Maximum Severity, Study Day Post Dose 1, and Treatment Group - Fosfomycin Safety Population

[Implementation note: Update footnote to use Fosfomycin Safety Population]

Table 44: Number and Percentage of Subjects Experiencing Solicited Adverse Events of Moderate Severity or Greater Over the Follow-up Period by Treatment Group and Severity - Safety Population

| Symptom | Severity | Strategy 1 (N=X) | | Strategy 2 (N=X) | | Odds Ratio (95% CI) ^b | P-Value ^b |
|-------------------|----------|------------------|---------------------|------------------|---------------------|----------------------------------|----------------------|
| | | n (%) | 95% CI ^a | n (%) | 95% CI ^a | | |
| Any Symptom | Moderate | x (x) | (x, x) | x (x) | (x, x) | x.x (x.x, x.x) | x.xxx |
| | Severe | x (x) | (x, x) | x (x) | (x, x) | | |
| Insomnia | Moderate | x (x) | (x, x) | x (x) | (x, x) | x.x (x.x, x.x) | x.xxx |
| | Severe | x (x) | (x, x) | x (x) | (x, x) | | |
| Headache | Moderate | x (x) | (x, x) | x (x) | (x, x) | x.x (x.x, x.x) | x.xxx |
| | Severe | x (x) | (x, x) | x (x) | (x, x) | | |
| Dizziness | Moderate | x (x) | (x, x) | x (x) | (x, x) | x.x (x.x, x.x) | x.xxx |
| | Severe | x (x) | (x, x) | x (x) | (x, x) | | |
| Nausea | Moderate | x (x) | (x, x) | x (x) | (x, x) | x.x (x.x, x.x) | x.xxx |
| | Severe | x (x) | (x, x) | x (x) | (x, x) | | |
| Vomiting | Moderate | x (x) | (x, x) | x (x) | (x, x) | x.x (x.x, x.x) | x.xxx |
| | Severe | x (x) | (x, x) | x (x) | (x, x) | | |
| Constipation | Moderate | x (x) | (x, x) | x (x) | (x, x) | x.x (x.x, x.x) | x.xxx |
| | Severe | x (x) | (x, x) | x (x) | (x, x) | | |
| Diarrhea | Moderate | x (x) | (x, x) | x (x) | (x, x) | x.x (x.x, x.x) | x.xxx |
| | Severe | x (x) | (x, x) | x (x) | (x, x) | | |
| Back Pain | Moderate | x (x) | (x, x) | x (x) | (x, x) | x.x (x.x, x.x) | x.xxx |
| | Severe | x (x) | (x, x) | x (x) | (x, x) | | |
| Rhinitis | Moderate | x (x) | (x, x) | x (x) | (x, x) | x.x (x.x, x.x) | x.xxx |

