14.3.1.2 Unsolicited Adverse Events

Figure 5: Frequency of Related Adverse Events by MedDRA System Organ Class and Severity - Fosfomycin Safety Population

[Implementation Note: A generic figure is shown below. This figure includes only unsolicited events of grade 2 and above for subjects in the Fosfomycin Safety population. A **horizontal** bar chart should be presented in 1 image file separate panels for each treatment group (2 columns (treatment groups)). Axes should be labeled as follows: y-axis label: System Organ Class, y-axis label: Number of Events. The treatment groups should be indicated in the panel headers including “(N=X)”, where N = the number of subjects in the in the Safety Population (Strategy 1 or Strategy 2. The y-axis should present all SOCs reported by at least 1 subject and an “All Events” category. Y-axis should be sorted with “All Events” first, then in decreasing order of total incidence.]

[figure not shown]
[figure not shown]

Figure 6: Incidence of Unsolicited Adverse Events by MedDRA System Organ Class and Severity - Fosfomycin Safety Population

[Implementation Note: A Generic figure is shown below. This figure includes only unsolicited events of grade 2 and above for subjects in the Fosomycin Safety population. A **horizontal** bar chart should be presented in 1 image file with separate panels for each treatment group (2 columns: Strategy 1 or Strategy 2). Axes should be labeled as follows: y-axis label: System Organ Class, x-axis label: Percentage of Subjects (%). The treatment groups should be indicated in the panel headers including “(N=X)”, where N = the number of subjects in the in the Safety Population. Subjects are counted at most once at the maximum severity across for any events in the applicable SOC. The y-axis should present all SOCs reported by at least 1 subject and an “All Events” category. Y-axis should be sorted with “All Events” first then in decreasing order of total incidence.]

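### Figure 6 and the by-day rule in SAP 9.3 use denominators that do not match the subjects in whom the adverse events were collected

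*SAP*

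**What the plan says.** **Unsolicited events.** SAP 9.3.2 states: "The unsolicited AEs will be collected only in the Fosfomycin Safety Population", that is, in subjects with at least two fosfomycin doses. SAP 9.3 limits unsolicited summaries to that population, and Tables 46–48 use it as N. The shell notes for Figures 5 and 6 (SAP Appendix 2) restrict the plotted events to the same population, but define the panel header as "N = the number of subjects in the in the Safety Population". Figure 5 is scaled in number of events, Figure 6 in percentage of subjects.

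**Solicited events by day.** The SAP gives several rules for the denominator:

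- SAP 9.3, for adverse events by day: "the denominator will be the number of subjects enrolled and not withdrawn from the study by the day being described".
- SAP 9.3.1, for summaries by arm: "the denominator will be the number of subjects who received at least one dose of the treatment with non-missing data for the event summarized".
- Table 42 note, carried over to Table 43: Safety Population subjects "with severity grades collected for each solicited symptom on the respective day(s".
- Table 40 note: Safety Population subjects for the symptom and day, without saying whether a grade must have been collected.

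**When solicited collection ends.** Protocol 9.2.2 says: "The solicited AEs will be collected after first dose of study product is given and until the EOT". For subjects on fosfomycin, SAP 9.3.1 says that "solicited AEs will be collected for 2 days after last dose of fosfomycin or until EOT, whichever occurs later". The same section then says: "Solicited events were recorded for trial Days 1-12, or until study completion or termination, as the maximum severity for each day". The shells of Tables 40 and 42 have columns through Day 12 and a further Day 13+ column.

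**The concern.** An incidence means what it says only if everyone in the denominator could have had the event recorded.

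In Figure 6 this fails by arm. Nearly all of Strategy 1 should reach two fosfomycin doses. Under the protocol, Strategy 2 subjects receive fosfomycin only through the single investigator-directed adjustment. Dividing by the whole Safety Population would make Strategy 2 look almost free of unsolicited events and would contradict Table 46.

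In the by-day tables, a subject past EOT has not withdrawn and stays in the Section 9.3 denominator until the test-of-cure visit (Day 21 + 7). If that subject is no longer being asked, daily rates fall because the questions stopped.

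The safety of fosfomycin is a secondary objective. Figures 5 and 6 and Tables 40–43 carry no asterisk, so under SAP Section 8 they go to the FDA in the abbreviated study report.

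**Working it through.** The documents give no safety incidence or denominator count, so there is no stated figure to reproduce. The check is the factor

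understatement = (N in the stated denominator) ÷ (N actually under collection).

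**Figure 6, if the percentage uses the header N**

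Inputs:
- 62 enrolled (SAP 5), randomized 1:1. Arm counts are not stated, so I assume 62 ÷ 2 = 31 treated per arm.
- The share of Strategy 2 switched to fosfomycin is not stated. I use 10–30%, guided only by the fluoroquinolone-resistance range in Protocol 2.1, with 50% as an outer case.

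One affected subject on the header N is 1/31 = 3.2%.

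| Strategy 2 switched | Subjects with ≥2 doses | One affected subject | Factor |
|---|---|---|---|
| 10% | 3 | 1/3 = 33% | 31/3 = 10.3 |
| 20% | 6 | 1/6 = 17% | 31/6 = 5.2 |
| 30% | 9 | 1/9 = 11% | 31/9 = 3.4 |
| 50% | 15.5 | 1/15.5 = 6.5% | 31/15.5 = 2.0 |

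In Strategy 1, if 28 to 31 of 31 take at least two doses, the factor is 31/28 = 1.1 down to 31/31 = 1.0.

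**Figure 5.** The plotted values are counts, so no percentage changes. Only the N in the header is wrong.

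**By-day tables, if the Section 9.3 rule is followed and collection ends at EOT (or two days after the last fosfomycin dose)**

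The factor on a given day is 1 ÷ (share still under collection). Assumptions, none of them stated in the documents as frequencies:
- unadjusted subjects take their last dose evenly on Days 5, 6 and 7, with EOT evenly 0, 1 or 2 days later;
- Strategy 1 has no adjustments, so collection runs to last dose + 2;
- 0–30% of Strategy 2 is adjusted at about Day 3 and then takes 7 further days (Protocol 7.3), with last dose on Day 9 or 10, half of them on fosfomycin;
- no withdrawals.

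For Strategy 1, collection then ends on Day 7, 8 or 9 with probability 1/3 each. For unadjusted Strategy 2, counting the nine dose-and-lag combinations gives 6/9 still asked on Day 7, 3/9 on Day 8 and 1/9 on Day 9.

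| Day | Strategy 1: share, factor | Strategy 2, 0% adjusted | Strategy 2, 30% adjusted |
|---|---|---|---|
| 5 | 1.00, 1.0 | 1.00, 1.0 | 1.00, 1.0 |
| 7 | 1.00, 1.0 | 0.67, 1.5 | 0.77, 1.3 |
| 8 | 0.67, 1.5 | 0.33, 3.0 | 0.53, 1.9 |
| 9 | 0.33, 3.0 | 0.11, 9.0 | 0.38, 2.6 |
| 10 | 0, nobody asked | 0, nobody asked | 0.28, 3.6 |

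If collection really ran through Day 12 for everyone, the share stays near 1 and the Section 9.3 denominator is nearly right until then. Only the Day 13+ column would still be exposed.

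**The case against.** A reader might infer that the SAP understates safety incidences several-fold across both figures and all by-day tables, mainly in Strategy 2. The documents do not support that.

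- **Figure 5** shows counts and cannot understate an incidence.
- **The by-day denominator is contested within the SAP.** Section 9.3.1 is the more specific text for solicited events. It asks for non-missing data, and repeats this in the paragraph that cites Tables 40 and 41. The Table 42 note already requires a grade collected that day. No by-day shell note adopts the Section 9.3 rule.
- **Collection may have run longer.** The Days 1–12 statement, an EOT window reaching Day 12, and a fosfomycin phone contact on Day 7–12 (+2) all leave open that many subjects were still being asked.
- **The arm pattern of Figure 6 does not carry over to the by-day tables.** Both arms are affected, and from Day 10 adjusted Strategy 2 subjects may be the only ones still under collection.
- **Figure 6 can be read correctly.** Its title and Section 9.3 point to the Fosfomycin Safety Population, and the note does not separately state a percentage denominator.

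These points stand, and they make both understatements conditional. They do not settle the matter. Non-missing data for an event is not a by-day condition: a subject with data on Days 1–7 still qualifies on Day 10. The Days 1–12 statement contradicts the EOT cutoff in the same section and does not cover Day 13+. In Figure 6, the only N written into the note is the wrong one.

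**Conclusion.** The point holds in two parts of different strength.

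The Figure 6 header N is wrong for the events plotted. If percentages follow it, Strategy 2 is understated about 3- to 10-fold and Strategy 1 by no more than about 1.1-fold. This rests on about 31 per arm and 10–30% switching to fosfomycin. At 50% switching the Strategy 2 factor is about 2.

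The by-day denominator is an unresolved contradiction, so two programmers could follow the SAP and report different percentages. If the Section 9.3 rule is used and collection stopped at EOT, rates are unaffected through Day 5, understated about 1.5- to 3-fold around Day 8, and generally by more later, in both arms. Those multiples are illustrative: they depend on EOT timing, on adjustments, and on whether collection ended at EOT or Day 12.

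The affected displays are descriptive. The per-subject solicited comparison (Table 38), the proportional odds analysis (Table 44) and the unsolicited tables (46–48) do not use either denominator.

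**What to change.** 1. In the notes to Figures 5 and 6, set the panel N to the Fosfomycin Safety Population in that arm, and state that it is also the percentage denominator in Figure 6, as in Table 46.
2. In SAP 9.3, replace the by-day sentence with the Table 42 rule: subjects with a severity grade, none/mild included, collected for that symptom on that day. Apply it to Tables 40–43 and align the Table 40 note.
3. Reconcile the EOT cutoff, the Days 1–12 recording statement and the Day 13+ column, so that it is clear which subjects were asked on each day.

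The cost is a few sentences of SAP text and shell notes. No new data are needed, and no other table changes.

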9.3.1. Solicited Events and Symptoms

Solicited AEs are AEs that are common following administration of these types of antibiotics. The solicited AEs will be collected after first dose of study product is given and until the EOT. If a subject is on fosfomycin, solicited AEs will be collected for 2 days after last dose of fosfomycin or until EOT, whichever occurs later.

Solicited events were recorded for trial Days 1-12, or until study completion or termination, as the maximum severity for each day. Only grade 2 and above solicited AEs will be reported. Target solicited events include insomnia, headache, dizziness, nausea, vomiting, constipation, diarrhea, back pain, rhinitis, pharyngitis, allergic reaction, candidiasis. The solicited events were measured by grading scales as defined in Table 3.

When calculating the incidence of solicited events, each subject will be counted once at the highest severity per day, and any repetitions will be ignored. For summaries presented separately for each treatment group, the denominator will be the number of subjects who received at least one dose of the treatment with non-missing data for the event summarized.

The number and percentage of subjects reporting at least one solicited adverse event of moderate severity or higher will be summarized for each solicited symptom and any symptom in Table 38 for the Safety analysis population. For each event, the denominator is the number of subjects in the applicable treatment group who received at least one dose of study product with non-missing data for the specific event. The 95% CIs calculated using Wilson methodology from a binomial distribution (SAS Proc Freq with a binomial option) will be presented. This analysis will be repeated in Table 39 to include subjects in the Fosfomycin safety analysis population who are those who received at least two doses of Fosfomycin.

For each systemic and any systemic event, the maximum severity over 12 days after the first dose will be summarized. The number and percentage of subjects reporting each event will be summarized by the maximum severity and treatment group. For each event, the denominator is the number of subjects who received the applicable treatment with non-missing data for the specific event. The 95% CI calculated using

Wilson methodology from a binomial distribution (SAS Proc Freq with a binomial option) will be presented [Table 40](#) for the Safety population and [Table 41](#) for the Fosfomycin safety population.

The proportion of subjects in each treatment group experiencing each solicited event will also be tabulated by day and severity level in [Table 42](#) for the Safety population and [Table 43](#) for the Fosfomycin safety population. Finally, solicited events will be analyzed by taking the most severe response over the follow-up period in [Table 44](#) for the Safety population and [Table 45](#) for the Fosfomycin safety population. Proportions for these derived binary variables will be reported along with 95% exact CIs. Comparisons of proportions by treatment groups will be given as odds ratio from the proportional odds model defined as:

$$\text{logit}(P(Y \leq j)) = \log\left(\frac{P(Y \leq j)}{P(Y > j)}\right) = \alpha_j + \beta \text{trt}$$
 where $j=0,1,2,3$ is the ordered severity with 0=None/Mild, 2 = Moderate, 3=Severe and $\text{trt}=1$ for strategy 1 and $\text{trt}=0$ for strategy 2. In order to interpret the model, the log of odds ratio (OR) can be expressed as

$\text{Log}[\text{odds}(\text{Severit} \leq j | \text{trt}=1) / \text{odds}(\text{Severit} \leq j | \text{trt}=0)] = \beta.$

Therefore, the odds ratio calculated as e^β can be interpreted as the odds ratio of having a maximum severity less than or equal to j for strategy 1 compared to strategy 2. The 95% CI for OR and associated p-value will be obtained from the above proportional odds model using the Wald Test.

The maximum severity occurrence of each solicited event (proportion of subjects for each severity level) will be plotted for each solicited adverse event [Figure 3](#) for the Safety population and in [Figure 4](#) for the Fosfomycin safety population. Solicited events by subject will also be presented ([Listing 10](#)).

